## **INTRODUCTION**

Although the prevalence of dental caries has been declined in industrialized countries, this disease continues to be widespread in the world especially in developing countries .Once it has become installed, it is of importance to use conservative procedures that simultaneously prevent caries progression and minimize healthy tooth structure wear . The most serious problem encountered during caries removal is anxiety, fear and pain. Pressure and heat during mechanical preparation and the annoying noise from the handpiece are to blame. Furthermore, Conventional caries removal involved the use of drilling often causes over preparation of sound healthy dentin because the drill remove infected and affected dentin, leading sometimes to pulp inflammation and even exposure.

This was perceived as unpleasant and painful by many patients, so local anesthesia had to be administered to control pain. System for caries removal and cavity preparation have been under strong pressure for development towards minimal invasive procedures and increased patient comfort.

During the last few decades, many alternative methods for cavity preparation and caries removal have been introduced, including atraumatic restorative treatment.

Atraumatic Restorative Treatment (ART) is a minimally intervention approach that concerned with preventive measures, sealing and filling cavities .The restorative technique needs the removal of the infected, softened and demineralized dentin by use of hand instruments, followed by the application of a chemical –adhesive material (1,2) for management of caries. This approach, that is an effective and economical method to prevent and control caries lesion progression, causes less dental anxiety and discomfort to the patients than conventional rotary instruments used in conventional restorative treatment.(3)

Initially, ART was recommended by the World Health Organization for escorting restorative care to people without access to dental services (2). ART was originally developed for economically underdeveloped populations with limited resources (4). It also has applications in industrial countries, however, especially for: very young children who are being introduced to oral care (5), patients who experience extreme fear or anxiety about dental Procedures(6,7), mentally and/or physically handicapped patients (7,8) ,home-bound elderly and nursing home resident patients (9,10) ,and patients from high-risk caries clinics who can benefit from ART as an intermediate treatment to stabilize conditions (5,11) .

ART has been proven to be a high quality and reliable approach in the management of dental caries, and became suitable for all patients, regardless of the economic and social situation (12,13)

ART has many advantages especially in pediatric dentistry as less anxiety, less pain and rarely requires local anesthesia (14).

A meta-analysis of ART showed that high-viscosity GICs presented higher clinical survival rates than conventional or medium-viscosity glass ionomers (15) so High-Viscosity Glass ionomer cements (GICs) is the most used material for the ART approach due to their biological, physical, and chemical properties (16). Notably, hand mixing of GICs might allow for an increased incidence of operator errors during material preparation, as the ratio of powder to liquid may vary according to manufacturer's recommendations(17). The quantity of powder dispensed varies according to powder packing density in the volumetric scoop. The volume of liquid dispensed from the manufacturer-supplied dropper bottle varies depending on the angle at which the bottle is held, the pressure applied to squeeze a drop, and the inclusion of air bubbles(17). With the purpose of decreasing these variables, encapsulated dental cements have been introduced in the market(18). These premade mixtures utilize mechanical mixing methods and allow standardization of the powder/liquid ratio in a sealed capsule, which is expected to reduce variation in clinical outcomes(18,19).

Resin modified GI are formulated by incorporating a small quantity of resin monomers and initiators into GI material in order to improve some of mechanical properties the clinical performance of RMGIs ,however, remain inferior to the resin composite material (20)

A novel restorative material has been developed as enhanced RMGIs (ACTIVA BIOACTIVE restorative).the resin monomer added to ACTIVA BIOACTIVE restorative are claimed to impart resilience to the material to improve its mechanical properties . this material are an esthetic fluorinated dental restorative material, with promising claims to be more bioactive and release more fluoride than glass ionomer cement (21) they are moisture friendly , transport water , and stimulate apatite formation at the material-tooth interface.in addition , these resins react to PH changes in the mouth by releasing and up-taking calcium ,phosphate and fluoride ions .

ACTIVA-BIOACTIVE restorative material claims to possesses characteristics of both composite and resin modified glass ionomer (RMGI) as strength, esthetics and physical properites of composites , Seals teeth against bacterial Leakage (22,23) and release and recharge more of calcium, phosphate and fluoride than glass ionomer (21) However, there is few studies evalute the clinical performance and mechanical properties of ACTIVA BIOACTIVE restorative material versus other restorative material .

## **AIM OF THE STUDY**

### **The aim of this study is :**

- 1-** Evaluate the fluoride release capacity and compressive strength of a new bioactive restorative material .
- 2-** Evaluate and compare the clinical performance and survival rates of bioactive restorative material with high viscosity glass ionomer in class I restoration performed using Atraumatic Restorative Treatment approach in primary molars.

[figure not shown]
[figure not shown]
## Materials and Methods

### In Vitro Study

#### Materials

|                |                                       |                              |
|----------------|---------------------------------------|------------------------------|
| Material name: | ACTIVA BIOACTIVE restorative material | Fuji IX                      |
| Manufacture:   | Pulpdent , Watertown, MA USA          | GC America                   |
| Material type: | Enhanced resin modified glass ionomer | High-viscosity glass ionomer |

#### Grouping of the specimens:

### Sample size:

The sample size estimation was done using Steven K. Thompson equation and assuming power 90% and effect size 0.05

$$n = \frac{N \times p(1-p)}{[N - 1 \times (d^2 \div z^2)] + p(1-p)}$$

With:-

n (sample size)

N (population size) = 90,000,000

p (probability value or p-value) = 0.11

z (standard score or z-score) = 1.96

d (difference between paired data or Effect Size) = 0.5

So the resultant **n = 28.07**

Sample size analysis for compressive strength and fluoride release testing was calculated to be 28 specimens that will be distributed as 7 in each experimental group (four groups) according to data collected from previous studies.

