### **II-Fluoride release :**

#### **\* Preparation of the specimens:**

Specimens will be prepared in split *Teflon* mold and then removed after one hour from mixing. The specimens will be finished and then coated with glass ionomer varnish and will be stored in water for 24 hours in an incubator at a temperature of 37 °C, then the specimens will be removed from the water and dried.

Each specimen will be immersed in deionized water in plastic bottles and will be stored in an incubator at 37°C till the time of testing. At the time of testing, each plastic bottle will be thoroughly shaken and then the specimen will be removed, dried and returned into a new bottle containing deionized water.

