#### **\*Testing procedures:**

The fluoride ion release will be measured after storage in deionized water for 1 day, 7 days, 1 month and 3 months using fluoride ion-selective electrode (ISE) attached to an ion meter.

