### **Statistical analysis**

Data will be collected, tabulated, and statistically analyzed using suitable statistical test to achieve the aim of this study .

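### The in vitro sample size of 28.07 does not follow from its inputs (the equation gives 1.5 or 150.4), the effect size is given two ways, and the 90% power claim has no basis

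*Combined protocol and SAP*

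**What the plan says.** The Sample size section of the In Vitro Study (under Grouping of the specimens) says the number was obtained from a named equation "assuming power 90% and effect size 0.05". The inputs listed under the equation are "N (population size) = 90,000,000", "p (probability value or p-value) = 0.11", z = 1.96 and "d (difference between paired data or Effect Size) = 0.5". The stated result is n = 28.07.

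The section then plans for "28 specimens that will be distributed as 7 in each experimental group (four groups) according to data collected from previous studies". No mean, SD or expected difference from those studies is given.

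Two laboratory outcomes are planned. Compressive strength is measured once, at 24 hours, by loading each specimen to fracture. Fluoride release is "measured after storage in deionized water for 1 day, 7 days, 1 month and 3 months". After each reading "the specimen will be removed, dried and returned into a new bottle containing deionized water", so the four fluoride readings come from the same specimens.

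The Statistical analysis section says only that data will be "statistically analyzed using suitable statistical test". It names no test and no significance level.

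**The concern.** Three things do not fit together. The effect size differs tenfold between the opening sentence and the input list. The reported 28.07 looks wrong for either value. The section also claims 90% power from an equation whose only terms are N, p, d and z.

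If so, the 28 specimens have no reproducible basis, and a reader cannot tell how large a difference between materials 7 specimens per group could detect. These tests are the first stated aim of the study. A non-significant laboratory comparison could then be read as equivalence on the strength of a power figure that was never calculated. For fluoride, the detectable difference also depends on how the four repeated readings are handled, which the plan does not say.

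**Working it through.** **Inputs** (all from the in vitro Sample size section): N = 90,000,000; p = 0.11, so p(1−p) = 0.11 × 0.89 = 0.0979; z = 1.96, so z² = 3.8416; d = 0.5 (input list) or 0.05 (opening sentence).

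**1. Trying to reproduce 28.07.** I read the denominator as the usual finite-population form:

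n = N·p(1−p) / [(N−1)(d²/z²) + p(1−p)]

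Because N is so large, this is almost exactly z²·p(1−p)/d².

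| d | z²·p(1−p)/d² | n |
|---|---|---|
| 0.5 | 3.8416 × 0.0979 / 0.25 | 1.50 |
| 0.05 | 3.8416 × 0.0979 / 0.0025 | 150.4 |
| Stated in the plan | – | 28.07 |

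As printed, the bracket can also be read literally as N − 1 × (d²/z²). That gives n = 0.098 for either d, so operator precedence does not explain the figure.

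**2. What would give 28.07?**
- Keeping p = 0.11: d = 1.96 × √(0.0979/28.07) = 0.116.
- Keeping d = 0.05: p(1−p) = 28.07 × 0.0025/3.8416 = 0.0183, so p = 0.0186.
- Keeping d = 0.5: p(1−p) = 28.07 × 0.25/3.8416 = 1.83. This is impossible, since p(1−p) cannot exceed 0.25. The largest n at d = 0.5 is 3.84, at p = 0.5.

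None of these values of d or p appears in the section. Replacing z by the sum of the two-sided 5% and 90% power quantiles gives 4.1 (d = 0.5) or 411.5 (d = 0.05). Other z values, and doubling or quadrupling the result, do not give 28.07 either.

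**3. Power.** The equation has no term for power or type II error; 1.96 is a 95% confidence quantile. The quantity labelled a p-value acts as a proportion, and d acts as a margin of error around it. Neither relates to a difference in means of a continuous measurement.

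**4. What 7 per group can detect (illustrative).** Inference: the four groups are two materials by two tests, so each comparison is 7 against 7. Assumptions: the effect is a standardised mean difference, and the test is a two-sided two-sample t-test with 12 degrees of freedom. Power comes from the noncentral t distribution with noncentrality SMD × √(7/2).

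| Two-sided alpha | Difference (SD) | Power |
|---|---|---|
| 0.05 | 0.05 | 5.1% |
| 0.05 | 0.5 | 13.9% |
| 0.05 | 1.89 | 90% |
| 0.0125 (0.05/4, Bonferroni over four fluoride times) | 1.9 | 72.2% |
| 0.0125 | 2.33 | 90% |

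The half-width of a 95% confidence interval for the difference is t(0.975, 12) × √(2/7) = 2.179 × 0.535 = 1.16 SD.

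**The case against.** The best defence is that 0.5 is a typing slip. The in vivo Sample size section uses the same template with 0.05 in both places. If so, the result of 1.5 and the 3.84 ceiling fall away. The discrepancy does not: the equation then gives 150.4 against a stated 28.07.

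Other points stand in part:
- The four groups can reasonably be inferred. There are two materials and two tests, and specimens crushed at 24 hours cannot serve for three months of fluoride measurement. The fault is that the plan does not say so.
- The 5% and 14% power figures depend on reading the stated effect size as a standardised mean difference, which the plan does not say. They do not show that 7 per group is too few. Differences between materials may be large, and with no SD or expected difference in the plan, adequacy is unknown.
- The first aim speaks of evaluating the new material, and only the second speaks of comparing. A t-test, a single key fluoride time and Bonferroni are reviewer choices; a repeated-measures model would be equally valid.
- This is bench work with no participants exposed. That limits the severity, but the plan chose to claim 90% power, and the claim should be true.

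**Conclusion.** The concern holds. On the stated inputs the equation gives 1.50 or 150.4, and 28.07 is not reproduced on any reading tried. The effect size is contradictory within one section, and correcting the apparent slip does not repair the result. The 90% power is unsupported because the equation cannot express power and does not address continuous outcomes. These conclusions need no assumption beyond the sensible reading of the bracket, and the literal reading fails too.

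The detectable differences of about 1.9 SD (one comparison at 5%) and 2.3 SD (four fluoride times with Bonferroni) rest on the inferred grouping and the assumed t-test. They are illustrations of what 7 against 7 can do, not findings about the plan. This should be fixed; confidence is high.

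**What to change.** In the in vitro Sample size section, delete the equation, its inputs and the claim of 90% power at 0.05 or 0.5. Define the four groups. If they are two materials by two tests, wording such as this would serve:

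> Seven specimens per material per test (28 in total). A two-sided 5% two-sample t-test has 90% power for a between-material difference of about 1.9 SD, for compressive strength and for fluoride release at one prespecified time point. The other fluoride times are descriptive.

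If all four fluoride times are to be tested, state about 2.3 SD with Bonferroni, or base the figure on a named repeated-measures model. The wording above gives each of the two outcomes its own 5%. Say that this is intended; splitting alpha between them (0.025 each) raises the 90% power difference to about 2.1 SD by the same calculation.

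Give the means and SDs from the previous studies and say whether the expected difference reaches the stated size. Name the test and alpha in the Statistical analysis section, and report between-material mean differences with 95% confidence intervals (half-width about 1.2 SD).

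The cost is protocol wording; the restatement needs no extra specimens. The downsides are a less favourable detectable difference and having either to choose one fluoride time in advance or to accept a larger difference. If the earlier data point to a difference smaller than the stated one, the number of specimens has to be reconsidered or the comparison presented as estimation only.

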### Methods:

#### I-Compressive strength

**\*Preparation of the specimens:** Specimens will be prepared in split Teflon mold according to ISO Guidelines specification No. 9917-1:2007(E) (24).

The material will be proportioned and mixed according to the manufacturer's instructions and then placed in special mold up to a slight excess. The mold will be closed and placed under pressure using a screw clamp. The whole assembly will be transferred to an incubator and maintained at a temperature of 37 °C. One hour after mixing, the specimens will be removed from the mold, finished using wet silicon carbide paper and stored in water in an incubator at a temperature of 37 °C until the time of testing.

### **\*Testing procedures:**

Compressive strength and for each material will be measured after 24 hours. Each specimen will be placed with the flat ends of the specimen between the platens of the universal testing machine and compressive load will be applied along the long axis of the specimen.

The load at fracture for each specimen, will be recorded and compressive strength will be calculated as follows (25) .

$$CS = 4P/\pi d^2$$

Where: p is the maximum load applied in Newtons.

d is the measured diameter of specimen, in millimeters.

### **II-Fluoride release :**

#### **\* Preparation of the specimens:**

Specimens will be prepared in split *Teflon* mold and then removed after one hour from mixing. The specimens will be finished and then coated with glass ionomer varnish and will be stored in water for 24 hours in an incubator at a temperature of 37 °C, then the specimens will be removed from the water and dried.

Each specimen will be immersed in deionized water in plastic bottles and will be stored in an incubator at 37°C till the time of testing. At the time of testing, each plastic bottle will be thoroughly shaken and then the specimen will be removed, dried and returned into a new bottle containing deionized water.

#### **\*Testing procedures:**

The fluoride ion release will be measured after storage in deionized water for 1 day, 7 days, 1 month and 3 months using fluoride ion-selective electrode (ISE) attached to an ion meter.

### **In Vivo study**

#### **Study Population**

Total of 60 participants will be included in this study. 30 of them will be treated with (ACTIVA BIOACTIVE) restorative material in ART, 30 will be treated with (High-Viscosity glass ionomer ) restorative material in ART.

#### **Inclusion Criteria:**

- 1-Children aged from 4 to 8 years old, in good general health
- 2-Children classified as class 3 or 4 based on Frankle et al. classification. (26)
- 3-The children have at least one primary molar with class I carious lesion.
- 3- Asymptomatic teeth (without spontaneous pain)

## **Exclusion Criteria:**

1. Medically compromised patient
2. Presence of pulp exposure, pain, mobility
3. Presence of swelling, abscess or fistula near the tooth
4. Not accessible carious lesion to hand instruments

## **Study design :**

The study will be two parallel group, double blinded randomized controlled clinical trial that based on CONSORT (consolidated standars of reporting trials) guideline (27).The selected participant according to inclusion and exclusion criteria will be randomly allocated in two groups using (Research Randomizer Program) .

## **Blinding**

All paticipant don't know the type of received restorative material (ACTIVA BIOACTIVE or Heigh -viscosity GI restorative material) and the outcome will be evaluted by a examiner other than operator who doesn't know the type of received restorative material also.

## **Study setting**

The study will be performed at pediatric Department and Dental Puplic Health Department of Faculty of Dentistry, Ain Shams University, and at the institute of Graduate Studies and Research, Ain Shams University.

## **Sample size**

The sample size estimation was done using Steven K. Thompson equation and assuming power 90% and effect size 0.05

$$n = \frac{N \times p(1-p)}{[N - 1 \times (d^2 \div z^2)] + p(1-p)}$$

With:-

n (sample size)

N (population size)=90,000,000

p (probability value or p-value) =0.07

z (standard score or z-score)=1.96

d (difference between paired data or Effect Size)=0.05

So the resultant **n = 60**

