### **Recruitment/Setting**

The all participants of this study have been selected after complete clinical examination has been done with full medical and dental history , history of medications and history of hospitalization. In patients who receive dental treatment as an usual care in clinics of Pediatric Dentistry and Dental Public Health Department at faculty of dentistry, Ain-Shams University.

Informed consent designed to include all data about dental procedures in this study and clear more details about time consuming in the procedure and follow up visits, used materials and adverse event of this procedure . All participants have the right to withdraw from this study at any time .The consent will be assigned from each patient by the patient's parents or guardians after explanation of the study.

The full mouth rehabilitation will be performed by postgraduate student registered at the master Degree at the Pediatric Dentistry and Dental Public Health Department Faculty of Dentistry, Ain- Shams University

All subjects receive instructions on oral health, particularly in relation to oral hygiene and sugar consumption.

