## **Sample Grouping**

The 60 participant will be randomly divided into two group according to used material as follow:

**Group I (control):** will consist of 30 teeth that will be restored with conventional Atraumatic restorative treatment (ART) using by high-viscosity glass ionomer (Fuji IX)

**Group II:** will consist of 30 teeth that will be restored with Atraumatic Restorative Treatment (ART) using ACTIVA BIO ACTIVE restorative material

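### The clinical sample size of 60 does not follow from its printed equation, which gives 100, and the stated 90% power for an effect of 0.05 comes neither from that equation nor from 30 children per arm

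*Combined protocol and SAP*

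**What the plan says.** The clinical Sample size section names an equation for a finite population and says the estimate was made "assuming power 90% and effect size 0.05". It lists a population N of 90,000,000, z = 1.96, "p (probability value or p-value) =0.07" and "d (difference between paired data or Effect Size)=0.05", and gives the result as n = 60.

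The Study Population section adopts that number: "Total of 60 participants will be included in this study", 30 per material. The design is not paired. Study design says "The study will be two parallel group, double blinded randomized controlled clinical trial", and Sample Grouping says "The 60 participant will be randomly divided into two group according to used material as follow", with 30 teeth in each.

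The plan gives no failure rate for either arm, no alpha or sidedness beyond what z = 1.96 implies, no primary time point among 3, 6 and 9 months, and no allowance for dropout, although Recruitment/Setting notes that "All participants have the right to withdraw from this study at any time". The Statistical analysis section names no test; data will be "statistically analyzed using suitable statistical test to achieve the aim of this study".

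**The concern.** There are two separate faults.

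- **Arithmetic.** Equation, inputs and answer are all printed, and the answer does not follow from the inputs.
- **Method.** The equation answers a different question. It gives the number of subjects needed to estimate one proportion p to within ±d. It has no term for power and no second arm. The labels show the mismatch: p is called a p-value but works as a proportion, and d is called a paired difference but works as a margin of error, in a trial with two unpaired groups.

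This section is the plan's only quantitative support for its clinical aim, which is to compare the survival of two restorative materials. A reader told that the trial has 90% power for an effect of 0.05 would take a non-significant result as good evidence that the materials last equally well. If the real power is near 10%, that result is the likely one even when the materials differ by that amount.

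**Working it through.** **1. The plan's own figure.** Inputs from the clinical Sample size section: N = 90,000,000, p = 0.07, z = 1.96, d = 0.05.

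n = N·p(1−p) / [(N−1)·(d²/z²) + p(1−p)]

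- p(1−p) = 0.07 × 0.93 = 0.0651
- d²/z² = 0.0025 / 3.8416 = 0.00065077
- n = 5,859,000 / (58,569.3 + 0.0651) = **100.04**, against 60 stated

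Variants do not give 60 either: z = 1.645 gives 70.5, d = 0.5 gives 1.0, and the equation exactly as typeset, with no bracket round N−1, gives 0.065. To reach 60, one input has to change: p to about 0.041, d to about 0.065, z to about 1.52, or N to about 148. None of these values is in the documents.

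**2. Power of 30 per arm for an effect of 0.05.** The plan does not define the effect scale, so several readings were tried. The main one assumes that 0.07 is the failure proportion in one arm, that 0.05 is an absolute difference, that alpha is two-sided 5%, and that all 60 children are evaluable. Power was found by enumerating every pair of failure counts and adding the binomial probabilities of those that reach significance.

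| Reading, 30 per arm | Uncorrected chi-square | Fisher exact |
|---|---|---|
| 7% vs 12%, two-sided 5% | 10.4% | 2.4% |
| 7% vs 2%, two-sided 5% | 9.0% | 0.9% |
| Any base rate 0–95%, plus 5 points, two-sided 5% | 6.1–10.6% | 0.3–4.0% |
| Same grid, one-sided 5% | 9.7–21.0% | 1.6–6.8% |

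Other readings of 0.05:

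- **Log-rank approximation, 7% vs 12%.** Hazard ratio = ln 0.88 / ln 0.93 = 1.76. Expected failures = 30 × 0.07 + 30 × 0.12 = 5.7. Power is about 10%; 90% needs about 131 failures.
- **Standardised difference of 0.05, two-sample t test.** Power 5.4%.
- **Most favourable figure found.** The normal approximation, one-sided, for 7% vs 2% gives 23.7%.

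**3. What 90% power would need for 7% vs 12%.** Per arm, (1.96 + 1.2816)² × (0.07×0.93 + 0.12×0.88) / 0.05² = 717; with the pooled variance under the null, 721. Using the equation's own answer of 100 children (50 per arm) would not help: power is 13.3% (chi-square) or 6.2% (Fisher).

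**4. What 30 per arm can show, if failure is near 7%.**

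- Expected failures: 30 × 0.07 = 2.1 per arm.
- 95% half-width for the difference, Wald: 1.96 × √(2 × 0.0651 / 30) = 0.129 with 7% in both arms, and 0.148 at 7% vs 12%. By the Newcombe method with 2/30 in each arm it is 0.154.
- The alternative to 7% that is detected with 90% power is about 40% (chi-square) or 44% (Fisher).
- With 24 evaluable per arm (20% loss, assumed), the Wald half-width at 7% in both arms is 0.144, and the detectable alternatives are about 45% and 49%.

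**The case against.** The best defence is that the magnitudes rest on reading 0.07 as a failure proportion, which the plan never says, and that the fault could be a misprint. The in vitro Sample size section has the same opening sentence but enters d = 0.5, so 0.05 may be a slip for a standardised 0.5. Thirty per arm also does have 90% power for a very large difference. The missing bracket could be an artefact of text extraction.

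What stands:

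- The per-arm figures are illustrations and should not enter the protocol until p is confirmed. The low power does not depend on 7%, however: no base rate gives more than 10.6% two-sided for a 5-point difference.
- A standardised effect of 0.5 would have about 49% power two-sided and 61% one-sided (normal approximation). That is better, but still well short of 90%.
- The 90% power against a failure rate of 40% or more is for an effect the plan does not claim. The criticism is tied to the stated effect of 0.05.
- The bracket is a typographical point only; the intended form is clear, and it is the form that gives 100.
- A misprinted input could rescue the 60. It could not rescue the power statement, because the equation contains no power. A single misread digit is also an unlikely explanation: p = 0.04 gives 59.0, and the in vitro calculation likewise fails to return its stated 28.07 from its own inputs (it gives 1.5, or 150 with d = 0.05).

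**Conclusion.** The concern holds on both counts. The printed inputs give 100, not 60, and the documents do not show which number is wrong. Separately, 90% power for an effect of 0.05 is unsupported: the equation cannot produce it, and 30 per arm gives between 0.3% and 10.6% two-sided for a 5-point difference, and under 25% on every reading of 0.05 tried, one-sided tests included. At an assumed 7% vs 12%, a non-significant result would occur about 90% of the time by chi-square (100 − 10.4) and about 98% by Fisher (100 − 2.4). The failure of the equation is certain. The exact power depends on a failure rate, an effect scale and a test that the plan does not state, but no choice tried brings it near 90%. This must be corrected before the comparison is interpreted.

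**What to change.** Keep 60 children and correct the text.

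1. In the clinical Sample size section, delete the statement of 90% power and effect size 0.05, and the derivation of n = 60.
2. Have the investigators confirm what p is, where it came from, and the actual basis for 60. Add no rationale that they cannot confirm. Replacing 60 by 100 is not a repair, since 100 is still a one-sample precision figure.
3. If the equation is kept for any purpose, label p as the expected proportion and d as the margin of error, bracket N−1, and print the result that its inputs give.
4. Name the test and alpha in Statistical analysis, then state what 30 per arm can show at the confirmed failure rate. If that rate is 7%, all 60 are evaluable and alpha is two-sided 5%, the text could read:

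> The sample of 60 was not derived from a power calculation. With 30 children per arm and about 7% failure, the 95% confidence interval for the difference in failure extends about 13 to 15 percentage points either side. Power of 90% exists only against a failure rate of about 40% (chi-square) or 44% (Fisher exact) in the other arm.

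5. Say that withdrawals and restorations without a success or failure result widen this. The outcome table sets codes 5 and 6 aside from both and leaves code 9 unclassified. How much is lost depends on the analysis chosen.
6. Report the difference in failure with its 95% confidence interval, and do not present a non-significant test as equal survival.

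The cost is protocol wording and one confirmation from the investigators. No extra children are needed, but the stated capability of the trial becomes much more modest.
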